4.2. Removal of Subjects From Therapy

4.2.1. Reasons for Withdrawal/Early Discontinuation

Any subject who discontinues from study treatment for any reason will have their study treatment discontinuation recorded.

Subjects may be withdrawn from the study after signing informed consent for the following reasons:

- Adverse event
- Lost to follow up
- Death
- Protocol violation
- Withdrawal of consent by subject
- Study terminated by Sponsor
- Other (eg, discretion of the Investigator)

If a subject withdraws from the study, the Investigator will complete and report the observations as thoroughly as possible up to the date of withdrawal including the date of last treatment and the reason for withdrawal.

If the subject is withdrawn due to an adverse event, the Investigator will follow the subject until the adverse event has resolved or stabilized.

All subjects who are withdrawn from the study should complete protocol-specified withdrawal procedures (Section 4.2.2).

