4.2.2. Withdrawal Procedures

Protocol-specified withdrawal procedures are the same as those performed at the Day 5 visit (Section 6.5).

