6.7. Protocol Deviations

The Investigator should conduct the study in compliance with the protocol agreed to by Sponsor and, if required, by the regulatory authority(ies), and which was given approval/favorable opinion by the IRB/EC.

A deviation to any protocol procedure, or waiver to any stated criteria will not be allowed in this study except where necessary to eliminate immediate hazard(s) to the subject. Sponsor must be notified of all intended or unintended deviations to the protocol (eg, inclusion/exclusion criteria, dosing, missed study visits) on an expedited basis.

The Investigator, or person designated by the Investigator, should document and explain any deviation from the approved protocol.

If a subject was ineligible or received the incorrect dose or investigational treatment, and had at least one administration of investigational product, data should be collected for safety purposes.

The Investigator should notify the IRB/EC of deviations from the protocol in accordance with local procedures.

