9. SAFETY ASSESSMENTS

9.1. Adverse Events

All clinical adverse events occurring after the subject signs the ICF and up to 90 days after the single dose of study medication, whether observed by the Investigator or reported by the subject, will be recorded on the Adverse Event eCRF page. Medical conditions (including laboratory values/vital signs that are out of range) that were diagnosed or known to exist prior to Informed Consent will be recorded as part of medical history. All SAEs are to be reported according to the procedures in Section 9.3 SAE Reporting-Procedure for Investigators. Always report diagnosis as the adverse event or SAE term. When a diagnosis is unavailable, report the primary sign or symptom as the adverse event or SAE term with additional details included in the narrative until the diagnosis becomes available. If the signs and symptoms are distinct and do not suggest a common diagnosis, report them as individual entries of adverse event or SAE. For events that are serious due to hospitalization, the reason for hospitalization must be reported as the SAE (diagnosis or symptom requiring hospitalization). A procedure is not an adverse event or SAE, but the reason for the procedure may be an adverse event or SAE. Preplanned (prior to signing the ICF) procedures or treatments requiring hospitalization for preexisting conditions which do not worsen in severity should not be reported as SAEs (see Section 9.2 for Definitions). For deaths, the underlying or immediate cause of death should always be reported as an SAE. In addition, any serious, untoward event that may occur subsequent to the reporting period that the Investigator assesses as related to study drug should also be reported and managed as an SAE.

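### Section 4.2.1 lets a dosed subject be withdrawn from the whole study for an adverse event or protocol violation, and nothing then requires the Day 30 and Day 90 assessments or, after an early exit, the 24-hour ones

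*Combined protocol and SAP*

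**What the plan says.** Section 4.2.1 opens by saying that stopping study treatment is recorded. It then moves to the level of the study: "Subjects may be withdrawn from the study after signing informed consent for the following reasons". The list that follows includes "Adverse event" and "Protocol violation". For a subject who withdraws, "the Investigator will complete and report the observations as thoroughly as possible up to the date of withdrawal".

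Two provisions extend this. Section 4.2.1 adds: "If the subject is withdrawn due to an adverse event, the Investigator will follow the subject until the adverse event has resolved or stabilized". Section 4.2.2 says: "Protocol-specified withdrawal procedures are the same as those performed at the Day 5 visit". The Section 6.5 list for that visit is physical examination, concomitant medication, NIHSS, mRS, adverse events and a PK sample.

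Two other sections bear on the point. Section 6.7 deals with subjects who were ineligible or received a wrong dose or treatment: if such a subject "had at least one administration of investigational product, data should be collected for safety purposes". Section 9.1 records adverse events "up to 90 days after the single dose of study medication", with no exemption for withdrawn subjects. Section 4.2.3 rules out replacement, and Section 11.2 rules out imputation.

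**The concern.** With one short infusion, an adverse event or a protocol violation can end treatment, but neither prevents a clinic visit or a phone call weeks later. A plan that lets either reason end study participation opens a route by which subjects with a complication, or with a deviation that followed one, leave before their late outcomes are known.

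Three things are at stake. The first is late neurologic and functional outcome (Day 30 NIHSS; Day 30 and Day 90 mRS), which serves a secondary objective. The second is detection of new treatment-emergent events, whose window in Section 11.6.1 runs to 30 days after dosing. The third arises for anyone withdrawn before 24 hours: the first scheduled postdose hematology and chemistry, and the only scheduled postdose angiography. If more infusions are stopped in one arm than in another, the loss will differ by arm as well.

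**Working it through.** The plan states no withdrawal rate, so there is no figure of its own to reproduce. The check has two parts.

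**1. What is still required after withdrawal (Sections 4.2.1, 4.2.2, 6.2, 6.5, 6.6, 6.7 and 9.1)**

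- *Day 5 list:* required as far as possible. It gives one NIHSS, one mRS and one adverse event check at exit. It contains no hematology, chemistry, coagulation or imaging.
- *Event that caused withdrawal:* followed until resolved or stable. This does not cover new events, nor subjects withdrawn for a protocol violation.
- *Ineligible or misdosed subjects:* Section 6.7 asks for safety data but names no visit and no duration. It does not mention other violations, such as use of a medication that Section 5.2 disallows after dosing.
- *Adverse events to 90 days:* Section 9.1 sets the window, but its method is evaluation and questioning at each visit, and no visit is required after withdrawal.
- *24-hour tests and scan (Section 6.2), Day 30 visit and Day 90 call (Section 6.6):* no section requires them of a withdrawn subject.

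Section 4.2.1 therefore ends general reporting at withdrawal, while Sections 6.7 and 9.1 assume that some collection continues. The text does not say which governs.

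**2. Size**

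Inputs: 12 active subjects per dose level in Cohorts 3 to 5, and 6 (or 12) in Cohorts 1 and 2 (Table 3.1).

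- Share of an active arm lost per subject: 1/12 = 8.3%; 1/6 = 16.7%.
- Two subjects: 2/12 = 16.7%; 2/6 = 33.3%.

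Illustration for mRS 0 or 1 at Day 90. The outcome rates and the number withdrawn are assumptions, as is the use of assessed subjects as the denominator. Let n be the arm size, g the number who truly score 0 or 1, and m the number withdrawn, all with poor outcomes. The true rate is g/n and the reported rate is g/(n − m).

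| n | g | True | m = 1 | m = 2 | m = 3 |
|---|---|---|---|---|---|
| 12 | 4 | 33.3% | 4/11 = 36.4% | 4/10 = 40.0% | 4/9 = 44.4% |
| 12 | 6 | 50.0% | 6/11 = 54.5% | 6/10 = 60.0% | 6/9 = 66.7% |
| 6 | 2 | 33.3% | 2/5 = 40.0% | 2/4 = 50.0% | not shown |

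The overstatement in these cases runs from 3.0 to 16.7 points. The direction depends on the assumption that the withdrawn subjects did badly. Without it, a reported 4/10 is compatible with anything from 4/12 = 33.3% (both missing subjects poor) to 6/12 = 50.0% (both good).

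For adverse events the safety set is everyone dosed. If that set is the denominator, a withdrawn subject whose new event goes unseen counts as event-free for that term, which lowers its percentage by 8.3 or 16.7 points.

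**The case against.** The case on the other side is substantial, and much of it stands.

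- A reader might infer that all data stop on the withdrawal date. They do not: the index adverse event is followed, and the exit visit collects NIHSS, mRS and adverse events.
- A reader might infer that these subjects are certain to lose their late outcomes. Withdrawal is permitted, not required. The list also contains death and loss to follow-up, so it can be read partly as a set of disposition codes. Section 6.5, whose heading covers discontinuation, says that nothing more is needed after discharge until Day 30, which hints that discontinued subjects return. A hint is not a requirement, and the same section treats subjects who withdraw from the study separately.
- A reader might infer that the intracranial hemorrhage counts would describe only subjects without trouble. They would not. Sections 11.1 and 11.6.6.1 keep a subject withdrawn after a recorded bleed in the counts with that event. Only undetected or later bleeds could be missed.
- A reader might infer that the stopping rules are weakened by missed late visits. Their windows in Section 3.1.6 (36 hours for sICH; hospitalization and up to 5 days for other major bleeding) close before Day 30. Exit before 24 hours is a narrower matter. The scheduled scan and hemoglobin could then be missed, but subjects are to stay in hospital for at least 24 hours and Section 8.2 allows extra imaging.
- All analyses are descriptive and the arms are small. An assumed 5 of 12 has an exact 95% interval of about 15% to 72%, wider than any shift shown above. That limits the practical weight of the bias, but it is no reason to accept an avoidable one.

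**Conclusion.** The point holds in limited form. As written, the protocol permits withdrawal from the whole study for an adverse event or a protocol violation, and requires neither the Day 30 and Day 90 assessments nor, after an early exit, the 24-hour tests and scan. Without imputation or replacement, late NIHSS and mRS and new treatment-emergent events up to Day 30 can be missing in a way related to outcome.

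The only size that follows from the plan itself is 8.3% of a 12-subject active arm, or 16.7% of a 6-subject arm, per subject lost. The shifts in mRS rate rest on assumed rates and on the withdrawn subjects doing badly. The documents do not show that such losses will occur, and they do not support a claim that recorded bleeding counts are biased or that missed late visits affect dose escalation stopping. This is an inexpensive improvement to make, not a flaw that undermines the design.

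**What to change.** In Section 4.2.1, define discontinuation of the infusion and withdrawal from the study as separate events. List adverse event and protocol violation only under the first. State that every dosed subject stays on the existing schedule (24-hour assessments, Day 30 visit, Day 90 call) unless consent is withdrawn, the subject is lost to follow-up or dies, or the sponsor ends the study. This also removes the open category of investigator discretion as a reason to leave the study, so the sponsor should make that choice knowingly. Align Sections 4.2.2, 6.5, 6.7 and 9.1 so that they agree on what is collected after the infusion stops and for how long. Do not require extra tests of subjects who withdraw consent.

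The cost is a wording change plus assessments already on the schedule, done for a few more subjects. It alters data collection only and does not bear on when an infusion is stopped.

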4.2.2. Withdrawal Procedures

Protocol-specified withdrawal procedures are the same as those performed at the Day 5 visit (Section 6.5).

4.2.3. Subject Replacement

Any subject who discontinues study participation before completing all study visits will not be replaced.

4.2.4. Subject Re-screening Procedures

Not applicable.

5. TREATMENTS ADMINISTERED

5.1. Investigational Products

The Investigator must ensure that the investigational product will be used only in accordance with the protocol.

DS-1040b Injection 10 mg/10 mL is transferred into IV infusion solution (0.9% Sodium Chloride Injection, USP), as shown in Table 5.1. The placebo for DS-1040b will be 0.9% Sodium Chloride Injection, USP. In order to maintain the blind, placebo solution will be administered in the same manner as the DS-1040b IV solution in the respective cohort. The detailed procedures for drug preparation will be provided separately in pharmacy manual.

DS-1040b IV solution will be administered as an initial 0.5-hour infusion (25% of the total dose) followed by a 5.5-hour continuous IV infusion (75% of the total dose). In each cohort, 8 to 16 subjects will be randomized in a ratio of 3:1 (active:placebo). The assignment of either active or placebo will be blinded to subjects, Investigators, and the CRO staff.

5.1.1. Method of Assigning Subjects to Treatments and Blinding

The randomization schedule will be produced by a statistician from the Biostatistics CRO, according to the specifications provided by the Sponsor statistician. A dummy schedule will be produced before the study start and will be checked by the Sponsor statistician. After approval of the dummy schedule, the Biostatistics CRO will modify the random generator and issue the final randomization to a Sponsor statistician not involved in this study, who will approve the final randomization.

Randomization will be blinded to the subjects, Investigators, and CRO staff.

Allocation of treatment by subject at the clinical site will be done by contacting the interactive response system (IxRS).

- In the case of an emergency where, in the opinion of the Investigator, discontinuation of study treatment is not sufficient and the study treatment must be unblinded in order to evaluate further course of action, the Investigator must make every effort to contact the PAREXEL Medical Monitor prior to unblinding a subject. In the rare event that contact with the PAREXEL Medical Monitor is not possible prior to unblinding, the Investigator reserves the right to unblind in a true emergency, where subject safety is at immediate risk. All sites will be provided with details on how to contact the IxRS for unblinding at the start of the study, and this process will be documented in the IxRS manual.
- Upon unblinding, the Investigator will complete the Emergency Unblinding by Investigator Form and will return it to Daiichi Sankyo Medical Monitor.
- If the emergency unblinding is needed as the result of an SAE, the SAE must be immediately reported, as defined in the protocol (Section 9.3).

5.1.2. Method of Assessing Treatment Compliance

Since DS-1040b and placebo IV infusions will be administered at the site, treatment compliance will not be monitored in this study. However, the time of administration and dose amount will be captured for each subject. Administration of study drug will be recorded in the eCRF.

5.1.3. Labeling and Packaging

DS-1040b Injection 10 mg/10 mL is provided in a clear glass vial. Details of the packaging and labeling of DS-1040b injection 10 mg/10 mL will be provided in the pharmacy manual.

Packaging and labeling will be performed in accordance with Good Manufacturing Practice.

5.1.4. Preparation

DS-1040b injection 10 mg/10 mL and placebo will be prepared according to the detailed procedures for drug preparation that are provided in the pharmacy manual.

Table 5.1: Treatment Preparation

Drug Level	Drug Product (solution in glass vial)	Active Treatment		Loading Dose (0.5-hour infusion, infusion rate: 0.83 mL/min)	Maintenance Dose (5.5-hour infusion, infusion rate: 0.23 mL/min)	Placebo (0.9% Sodium Chloride Injection, USP)
		Drug Product Solution Volume	Additional 0.9% Sodium Chloride Injection, USP Volume			
0.6 mg	10 mg/10 mL	0.6 mL	99.4 mL	0.15 mg in 25 mL	0.45 mg in 75 mL	100 mL
1.2 mg	10 mg/10 mL	1.2 mL	98.8 mL	0.30 mg in 25 mL	0.90 mg in 75 mL	100 mL
2.4 mg	10 mg/10 mL	2.4 mL	97.6 mL	0.60 mg in 25 mL	1.8 mg in 75 mL	100 mL
4.8 mg	10 mg/10 mL	4.8 mL	95.2 mL	1.2 mg in 25 mL	3.6 mg in 75 mL	100 mL
9.6 mg	10 mg/10 mL	9.6 mL	90.4 mL	2.4 mg in 25 mL	7.2 mg in 75 mL	100 mL

5.1.5. Storage

Drug supplies must be stored in a secure, limited access storage area under the recommended storage conditions.

- DS-1040b Injection 10 mg/10 mL should be stored up to 25°C (excursions permitted up to 30°C).
- DS-1040b IV solution in-use stability will be provided in the pharmacy manual.

In the event of an excursion from storage requirements, the site will quarantine the Investigational Product and consult the Sponsor to determine whether the Investigational Product can be used.

5.1.6. Drug Accountability

When a drug shipment is received, the Investigator or designee will check the amount and condition of the drug, check for appropriate local language in the label, drug expiration date, and sign the Receipt of Shipment Form provided. The Receipt of Shipment Form should be faxed as instructed on the form. The original will be retained at the site. In addition, the Investigator or designee shall contact the Sponsor as soon as possible if there is a problem with the shipment.

A Drug Accountability Record will be provided for the investigational product. The record must be kept current and should contain, the dates and quantities of drug received, subject's (identification number and/or initials or supply number as applicable), for whom the investigational product was dispensed, the date and quantity of investigational product dispensed and remaining, if from individual subject drug units as well as the initials of the dispenser.

At the end of the study, or as directed, all DS-1040b, including unused, partially used, or empty containers, will be destroyed at the site. In the event a site cannot destroy the DS-1040b, it will be returned to a designee as instructed by Sponsor. Investigational Product will be destroyed or returned only after the study monitor has completed a final inventory to verify the quantity to be destroyed or returned. The return of Investigational Product must be documented and the documentation included in the shipment. At the end of the study, a final Investigational Product reconciliation statement must be completed by the Investigator or designee and provided to the Sponsor. Unused drug supplies may be destroyed by the Investigator when approved in writing by Sponsor and Sponsor has received copies of the site's drug handling and disposition Standard Operating Procedures (SOPs).

All investigational product inventory forms must be made available for inspection by a Sponsor authorized representative or designee and regulatory agency inspectors. The Investigator is responsible for the accountability of all used and unused study supplies at the site.

5.1.7. Retention Samples

There will be no retention sample taken during this study.

5.2. Concomitant Medications

For the specified number of days prior to enrollment and through study completion or upon early withdrawal, the following medications are not allowed:

Prior to enrollment (Day 1):

- Heparin use within 48 hours or elevated partial thromboplastin time.

- Nonvitamin K antagonist oral anticoagulant use within 48 hours such as dabigatran, rivaroxaban, apixaban, or other factor Xa inhibitors.
- Fondaparinux or low molecular weight heparin use within 48 hours at an anticoagulation dose.

Within 24 hours postdose period:

- Antiplatelet agents (aspirin, clopidogrel). After 24 hours post dose, use of antiplatelet agent will be at the discretion of the Principal Investigator.

Within 48 hours postdose period:

- Heparin, nonvitamin K antagonist oral anticoagulant such as dabigatran, rivaroxaban, apixaban, or other factor Xa inhibitors.

During the study, concomitant medications required to treat TEAEs will be permitted. Other concomitant medications for preexisting conditions (ie, hypertension, diabetes, etc.) are permitted, unless otherwise specified above. Concomitant medication usage will be at the discretion of the Principal Investigator.

Any medication (other than study drug) taken by subjects during the course of the study will be recorded and coded using the World Health Organization (WHO) drug dictionary.

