4.1.2. Exclusion Criteria

Subjects who meet any of the following criteria will be disqualified from entering the study:

1. Subjects have evidence of intracranial hemorrhage on noncontrast CT (or MR).
2. Subjects have symptoms of subarachnoid hemorrhage, even with normal CT.
3. Subjects have evidence of large MCA territory infarction (sulcal effacement or blurring of gray-white junction in greater than 1/3 of MCA territory).
4. Subjects have prior non-traumatic intracranial hemorrhage.
5. Subjects have known arteriovenous malformation or aneurysm.
6. Subjects have evidence of active bleeding.
7. Subjects have platelet count < 100,000.
8. Subjects have INR > 1.7.
9. Subjects have used heparin within 48 hours or have an elevated partial thromboplastin time.
10. Subjects have used a nonvitamin K antagonist oral anticoagulant such as dabigatran, rivaroxaban, apixaban, or other factor Xa inhibitors within 48 hours.
11. Subjects have used fondaparinux or low molecular weight heparin at an anticoagulation dose within 48 hours.
12. Subjects with anticipated use of heparin, or fondaparinux or low molecular weight heparin, or nonvitamin K antagonist oral anticoagulant such as dabigatran, rivaroxaban, apixaban, or other factor Xa inhibitors within 48 hours of randomization.
13. Subjects have blood pressure > 185/110 mmHg, or require aggressive medication to maintain blood pressure below this limit (routine medical treatment is allowed to lower the blood pressure below this limit).
14. Subjects have had intracranial surgery, clinically significant head trauma (in the opinion of Principal Investigator), Alteplase treatment, or a previous stroke within 3 months.
15. Subjects have had major surgery within 14 days.
16. Subjects have had gastrointestinal or genitourinary bleeding in the last 21 days.
17. Subjects have had a lumbar puncture (or epidural steroid injection) within 14 days.
18. Subjects have a preexisting disability classified by mRS > 1.
19. Subjects have an estimated glomerular filtration rate (using Modification of Diet in Renal Disease [MDRD] equation) < 60 mL/min/1.73 m².
20. Subjects have baseline hemoglobin < 10.5 g/dL.

21. Subjects have a positive pregnancy test. Serum pregnancy tests will be performed in women of childbearing potential (childbearing potential is assumed in women up to 55 years of age).

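### Section 5.2 omits fondaparinux and low molecular weight heparin from its 48-hour postdose prohibited list, so a start not anticipated at entry is not clearly prohibited

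*Combined protocol and SAP*

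**What the plan says.** Section 5.2 has three lists of prohibited medication. The list for the time before enrollment covers heparin, nonvitamin K oral anticoagulants and, as its own bullet, "Fondaparinux or low molecular weight heparin use within 48 hours at an anticoagulation dose". The list for the first 24 hours after dosing covers antiplatelet agents, which are then left to the Principal Investigator. The list for the first 48 hours after dosing reads "Heparin, nonvitamin K antagonist oral anticoagulant such as dabigatran, rivaroxaban, apixaban, or other factor Xa inhibitors" and stops there.

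Exclusion 12 in Section 4.1.2 rules out "Subjects with anticipated use of heparin, or fondaparinux or low molecular weight heparin, or nonvitamin K antagonist oral anticoagulant" within 48 hours of randomization. It carries no dose limit. Exclusion 11, which concerns prior use, is limited to an anticoagulation dose.

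Section 5.2 closes with a general provision: "Concomitant medication usage will be at the discretion of the Principal Investigator". Under Section 6.7, deviations "will not be allowed in this study except where necessary to eliminate immediate hazard(s) to the subject", and "Sponsor must be notified of all intended or unintended deviations to the protocol" on an expedited basis.

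**The concern.** Exclusion 12 is a judgement made before the infusion. Once the subject is dosed, Section 5.2 tells the site what may not be given, and it is silent on two anticoagulants that the protocol otherwise keeps away from study drug. If a need for anticoagulation arises that was not foreseen at entry, a site following the text could start LMWH or fondaparinux within hours of the infusion.

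Two things are at stake. The first is bleeding risk in subjects with a fresh infarct who have just received a drug intended to enhance fibrinolysis. The second is how the dose-escalation data are read. Section 3.1.6 stops escalation on 2 sICH cases in active-treated subjects at a dose level, or 4 across dose levels, within 36 hours of the start of infusion. It also stops on 2 non-ICH major bleeds per dose level during hospitalization and up to 5 days from the start of infusion. With counts this small, an anticoagulant started in the window makes it harder to attribute a bleed to DS-1040b. If the start is not a deviation, the sponsor would also not receive the expedited notice that a heparin start would prompt.

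**Working it through.** The plan gives no figure on this point, so the check is a comparison of the lists, followed by a check of the time windows.

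**Step 1: which drugs appear where.**

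| Place | Applies to | Heparin | Nonvitamin K oral anticoagulants | Fondaparinux / LMWH |
|---|---|---|---|---|
| Exclusions 9, 10, 11 | Use in the 48 hours before entry | Yes (9) | Yes (10) | Yes (11), anticoagulation dose |
| Exclusion 12 | Use anticipated within 48 hours of randomization | Yes | Yes | Yes, no dose limit |
| Section 5.2, before enrollment | Use within 48 hours | Yes | Yes | Yes, anticoagulation dose |
| Section 5.2, 48 hours postdose | Use after dosing | Yes | Yes | **Not named** |

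The only empty cell is the one that governs conduct after dosing.

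**Step 2: can the postdose bullet be read to cover them anyway?**

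- The word heparin could be stretched to take in LMWH. But exclusions 9, 11 and 12 and the pre-enrollment list all name LMWH apart from heparin.
- The closing reference to other factor Xa inhibitors could be stretched to take in fondaparinux. But that phrase ends a list of examples of oral anticoagulants, and exclusion 12 uses the same phrase while still naming fondaparinux.
- The opening sentence of Section 5.2 runs through study completion, which might seem to carry the pre-enrollment bullet forward. But that bullet sits under a heading for the time before enrollment, and the postdose periods have lists of their own.

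None of these supplies a clear postdose prohibition. At best the text is ambiguous.

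**Step 3: do the windows overlap?** Section 6 counts postdose times from the start of administration, unless otherwise specified. The sICH window in Section 3.1.6 runs 36 hours from the start of infusion. On that clock, a 48-hour ban spans the whole sICH window with 48 − 36 = 12 hours to spare. If a site counted from the end of the 6-hour infusion, the ban would end at 6 + 48 = 54 hours and would still span it. It would cover only part of the major-bleeding window, which can reach 5 × 24 = 120 hours.

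**Step 4: does exclusion 12 close the gap?** It closes it for planned use. Its clock starts at randomization, which falls after stroke onset and so at most 8 hours before the infusion under inclusion criterion 3. Its window therefore reaches at least 48 − 8 = 40 hours from the start of infusion, beyond the 36-hour sICH window. What it leaves open is use that was not anticipated when eligibility was judged.

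**The case against.** The strongest reply is that this is a one-line drafting mismatch with little practical effect. Much of that stands.

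- Exclusion 12 already removes planned use and shows that the sponsor meant to keep these drugs out for 48 hours. A site could reasonably read the postdose bullet in that light.
- Medication is recorded on Days 2, 3 and 4 for subjects still in hospital and at Day 5, early discharge or discontinuation. Section 5.2 also requires any medication taken during the study to be recorded.
- An sICH would very likely meet a criterion for a serious adverse event. Section 9.3.1 requires a report within 24 hours of awareness, with relevant concomitant medication in the narrative. The cases that could affect the stopping count would thus reach the sponsor quickly, with the exposure described.
- A met stopping criterion leads to an in-depth review of all safety data, which can take anticoagulant exposure into account.
- Counting every sICH errs on the cautious side. Nor is the window meant to be free of all antithrombotic drugs, since antiplatelet agents are allowed after 24 hours.

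These points limit the harm. They do not supply the missing prohibition.

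A reader might also infer a wider gap. The limit in "Other concomitant medications for preexisting conditions (ie, hypertension, diabetes, etc.) are permitted, unless otherwise specified above" is attached only to preexisting conditions, while "During the study, concomitant medications required to treat TEAEs will be permitted" and the sentence on investigator discretion carry none. That could suggest that even listed drugs may be given for an adverse event or at discretion. The documents do not support this. Section 5.2 opens by stating that the listed drugs are not allowed. Its antiplatelet bullet grants discretion only after 24 hours, which would be pointless if discretion already overrode the bans. Section 6.7 excepts only immediate hazards. Discretion therefore applies to what is not prohibited. On the plain text, that includes fondaparinux and LMWH after dosing.

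**Conclusion.** The omission is real and the text does not resolve it. An unanticipated postdose start of fondaparinux or LMWH is not clearly prohibited, and not clearly a deviation under Section 6.7, although it may fall within the 36-hour sICH window. It would go too far to say that such a start certainly breaches no rule, because a broad reading of the postdose bullet is weak but not excluded.

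The effect cannot be sized. The documents give neither the frequency of unanticipated use nor the sICH risk it would add. It is likely small, given exclusion 12 and the recording, reporting and review provisions. A reader might try to gauge it by how far one extra sICH moves a two-case stopping rule. That would show only that the rule is sensitive to any single case from any cause, and nothing about how often this gap would produce one.

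The conclusion rests on the wording of Sections 4.1.2, 5.2 and 6.7 and on the Section 6 convention for postdose time. It is a cheap improvement, not a flaw that threatens the trial.

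**What to change.** Add fondaparinux and low molecular weight heparin to the 48-hour postdose bullet in Section 5.2, so that it names the same drugs as exclusion 12.

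Have the sponsor state the dose scope, and state it identically in the bullet and in exclusion 12: either all doses, as exclusion 12 now reads, or anticoagulation doses only, as in exclusion 11. The documents do not settle which is intended after dosing, and the choice is the sponsor's. The second option would also require an edit to exclusion 12.

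The sentences on medication for adverse events and on investigator discretion need no change.

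The cost is a wording amendment, with no new data, visits or subjects. The downside is a small limit on investigator discretion over early anticoagulation. Emergencies remain covered by the immediate-hazard exception in Section 6.7.
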